6.5. POOLING OF CENTERS

Subjects will not be pooled based on site size, but rather by region, to ensure a sufficient number of subjects per treatment arm in both the ITT and PP populations for analysis that contain region as a model effect. The tables below show which countries comprise each of the regions to be used in analysis.

Region	Country
Europe	Germany
	Poland
	Spain
North America	United States

7. DEMOGRAPHIC, OTHER BASELINE CHARACTERISTICS AND MEDICATION

7.1. SUBJECT DISPOSITION AND WITHDRAWALS

Subject disposition data will be listed. A disposition table will present, by treatment group and overall, the number and/or percentage of subjects who signed the informed consent and entered the study (i.e., were screened, screen failed prior to Run-in, screen failed during the Day -14 to Day -1 Run-in, and randomized), complete the study drug dosing, discontinued study drug dosing, completed the study, and discontinued from the study after randomization. The reasons for early withdrawal after randomization will be summarized.

Assignment to the analysis sets (safety, ITT, and PP) will be summarized.

7.2. SUBJECT ELIGIBILITY AND PROTOCOL DEVIATIONS

All subjects, including screen failure subjects, who violate the Inclusion/exclusion criteria will be listed. Reason for screen failure will be summarized.

Deviations that could affect the primary and secondary variables will be considered when determining a subject's eligibility for the PP population. The number and percent of subjects who had any major deviation and each type of major protocol deviation will be tabulated for the ITT Analysis Set. All deviation term and class will be listed.

7.3. DEMOGRAPHIC AND OTHER BASELINE CHARACTERISTICS

Demographic characteristics include age, gender, race, ethnicity and country of investigational site. Baseline characteristics include baseline HbA_{1c} values, blood pressure, height, body weight, BMI, FPG, eGFR, eGFR at baseline categories (≥ 90 or < 90 mL/min/1.73 m²), duration of diabetes from diagnosis to the date of informed consent, and prior anti-diabetic treatment status at screening (including type of therapy used [metformin, sulfonylurea, DPP-4 inhibitor, alpha-glucosidase inhibitor etc.]). Randomization stratification related factors will be summarized based on data collected on CRF or by lab. They include HbA_{1c} values at baseline ($< 8.5\%$ vs. $\geq 8.5\%$), background anti-diabetic treatment status (metformin-only or metformin-and-OHA), eGFR at screening, and eGFR at screening categories (≥ 90 or < 90 and ≥ 60 mL/min/1.73 m²). Stratification factors from IWRS will be summarized. Summary descriptive statistics by treatment will include counts and percentages for discrete variables and estimation of means, standard deviations, medians, inter-quartile range (Q1, Q3), minimum, and maximum for continuous variables. Subjects' baseline demographic and personal baseline characteristics will be summarized by treatment group and overall for subjects in the Safety, ITT, and PP Analysis Set. Subject age at screening visit collected on CRF will be used.

Demographics data and randomization stratification factors will be presented in a data listing. Prior treatment will be listed along with all medications.

7.4. MEDICAL HISTORY

Significant medical and surgical history, including dates of diagnoses and procedures and whether the condition is ongoing, if applicable, will be collected. Each condition will be recorded as a verbatim term, date of onset, date resolved, and a checkbox that indicates ongoing conditions. Significant surgical and medical history will be coded using the Medical Dictionary for Regulatory Activities (MedDRA) Version 19.0.

Medical and surgical history will be summarized for the Safety Analysis Set by treatment group, system organ class (SOC), and MedDRA preferred term (PT), overall. Subject data will be listed.

Subject diabetes and cardiovascular diseases history will be summarized for all categorical variables by frequency and percentage. Listing will be provided.

7.5. MEDICATION

All prescription and over-the-counter medications, including vitamins and herbal supplements, that subjects receive during the trial must be documented on the CRF. The medication name, dose, frequency, route of administration, date(s) of administration and reason for administration must be recorded. This documentation should continue through the treatment period and the follow up period. Changes from baseline anti-hypertensive therapy and their rationale must be recorded in the CRF.

All medication will be coded using the World Health Organization Drug Dictionary (WHO-DD) version Enhanced B2 format. Preferred drug name, Anatomical/Therapeutic/Chemical (ATC) class will be reported for inclusion in the database.

Medication summaries based on ATC level 2, and the preferred drug names will be produced for the Safety Analysis Set. The summaries will present, by treatment group, the frequency and percentage of subjects who used any medication in an ATC class, or any medication based on a single preferred drug name. Subjects will be counted only once for each medication class and each preferred drug name.

For subject listings, medications will be reported based on ATC class and PT; multiple medications for an individual subject will be listed by start date and then by stop date, from earliest to latest medications.

7.5.1. Prior Medication

Any medication with a stop date prior to or on first dose date for the double-blind treatment period will be considered a prior medication.

No summary for prior medication will be presented. Prior and concomitant medications will be presented together on a single listing. The listing will be ordered by subject number and medication start/end dates. Prior medication will be flagged.

7.5.2. Concomitant Medication

A concomitant medication is any medication that the subject has taken in any time during the study treatment period. In the case of completely missing stop date, medication will be assumed to be concomitant.

All medication should be recorded in the concomitant medication log. Any medication given to treat hyperglycemia and continued for more than 2 weeks during the efficacy evaluation period of 60 weeks is considered a rescue therapy. Increase total daily dose of metformin, the background hypoglycemic therapy, during the treatment period is not allowed. However, if the dose of metformin is intensified during the double-blind treatment period for more than 2 weeks before the week 60 assessment, or study treatment stops if subject dropped out before week 60, it is also considered as rescue medication. All medications given to treat hyperglycemia will be recorded as concomitant medications in CRF.

Concomitant medications will be presented in a summary table as well as in a subject listing. Rescue medications will be summarized in a separate table and flagged in the same listing.

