3.3.3.3 Intensification of Medical Therapy for Hyperglycemia

During the entire treatment period, a review of diet and exercise counseling is suggested prior to prescription of rescue medication in the absence of specific medical indications for rescue medication.

Intensification of medical therapy for hyperglycemia is suggested during the treatment period if, after diet and exercise counseling, subjects meet the following glycemic criteria:

1. More than 3 consecutive, daily, fasting SMBG measures are ≥ 270 mg/dL (15 mmol/L) from baseline to week 6, ≥ 240 mg/dL (13.3 mmol/L) after week 6 to week 12, or ≥ 200 mg/dL (11.1 mmol/L) after week 12 to week 96
2. Fasting SMBG values are ≥ 250 mg/dL (13.9 mmol/L) and associated with clinical signs or symptoms of hyperglycemia (*e.g.*, weight loss, blurred vision, increased thirst, or increased urination, or fatigue), and the signs or symptoms are severe

From week 0 to week 6, up-titrating glimepiride dose to next higher level should be considered prior to prescribing rescue medication for hyperglycemia. If necessary, increases in glimepiride dosing can occur before the scheduled study visits. The criteria for glimepiride up-titration are provided in [Section 3.3.2.1](#). After glimepiride up-titration to the maximal level, rescue medication should be initiated for treating hyperglycemia based on investigator's assessment.

After week 6 of treatment, no further increases in glimepiride will occur. Therefore, from weeks 7 to 96, rescue medication for hyperglycemia should be prescribed by the investigator when deemed necessary for the well-being of the subject.

If a rescue medication for hyperglycemia is to be prescribed, a blood sample must be drawn prior to the administration of the rescue medication so that a final HbA1c value can be ascribed to the latest date upon which the subject's glycemic control will be impacted by the rescue medication.

The investigator may provide rescue treatment with any approved medication for diabetes that is not otherwise contraindicated, with the exception of SGLT2 inhibitor, sulfonylurea

and metformin, as all study subjects will already be taking metformin and may be taking active SGLT2 inhibitor or glimepiride through study participation.

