6.15 Concomitant Medication Assessments

A concomitant medication is any medication that the subject has been taking prior to enrollment and that the subject is expected to continue to take for some portion of the trial, as well as any medication other than the investigational product that the subject takes during the course of the trial.

The medications or treatment for controlling hypoglycemia must be recorded as concomitant medications in the CRF. Any medication given to treat hyperglycemia and continued for more than 2 weeks is considered a rescue therapy and should be recorded in the concomitant medication log.

Changes from baseline anti-hypertensive and anti-hyperlipidemia therapies and their rationale must be recorded in the CRF.

All prescription and over-the-counter medications, including vitamins and herbal supplements, that subjects receive during the trial must be documented on the CRF. This documentation should continue until the subjects complete the study.

Concomitant medications will be coded using the World Health Organization Drug Dictionary (WHO-DD). A table of concomitant medications based on the anatomic therapeutic chemical classification (ATC) and preferred name will be produced. A listing of concomitant medications will include all medications taken by any subjects during the course of the study.

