8.2.4. Sensitivity analysis

For all secondary analysis of body weight and SBP, missing data will be imputed via multiple imputations, following which the MMRM will be repeated on the complete datasets with results combined across complete datasets using standard multiple imputations techniques; Values collected after the start of rescue medication will be considered missing. Imputation steps include:

- a. Create monotone missing data as step a of section 8.1.1 with 100 imputed datasets;
- b. Regression approach under MAR will be used to generate complete datasets. The predictors for the regression imputation model at any time point will be region, treatment background (metformin only or metformin and OHA), baseline eGRF (≥ 90 or < 90 ml/min/1.73 m²), treatment, and values at all previous time points, including baseline. Values at each visit will be imputed sequentially. The first imputed values for subjects in bexagliflozin arm will be penalized by the mean improvement at week 60 on that endpoint (i.e. the mean change from baseline at week 60). Imputed values for subjects in glimepiride will not be penalized. Imputed values after the first missing value will be penalized through regression on first penalized value.
- c. Imputed datasets will be analyzed and results combined as in step c in section 8.1.1.

For the sensitivity analyses of proportion of subjects with hypoglycemia event, to account for subject discontinuation, incidence rate will be analyzed using negative binomial regression model. Data collected after the start of rescue medication will be considered as missing. The number of severe or documented symptomatic

hypoglycemia events will be used as outcome. Model will include region, treatment background (metformin only or metformin and OHA), baseline eGRF (≥ 90 or < 90 ml/min/1.73 m²), treatment, and baseline HbA_{1c} as fixed effect and the logarithm of the duration from first dose of double-blind treatment to date of week 96 visit as offset. If subject discontinued before week 96 visit, the date of discontinuation will be used. If subject used rescue medication, the last date before rescue medication will be used. The adjusted mean incidence over 96 weeks, 95% CI for each treatment arm, the risk ratio, 95% CI, and p-value will be presented.

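### The SAP recognises rescue therapy only within the first 60 weeks, so the 96-week hypoglycemia sensitivity analysis that is meant to drop post-rescue data cannot drop it after late rescue

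*SAP*

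**What the plan says.** **Rescue definition.** Under SAP 7.5.2, medication given for hyperglycemia and taken for more than 2 weeks "during the efficacy evaluation period of 60 weeks is considered a rescue therapy". An increase in metformin also counts as rescue, but only if the dose is "intensified during the double-blind treatment period for more than 2 weeks before the week 60 assessment" (or before study treatment stops, for subjects who drop out earlier). The SAP gives no other definition.

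**Analysis that uses it.** For the third key secondary endpoint, SAP 8.2.4 plans a sensitivity analysis in which "incidence rate will be analyzed using negative binomial regression model". The offset runs from first double-blind dose to the week 96 visit. On rescue, "Data collected after the start of rescue medication will be considered as missing", and for the end of follow-up, "If subject used rescue medication, the last date before rescue medication will be used".

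**Protocol.** Section 3.3.3.3 states that "from weeks 7 to 96, rescue medication for hyperglycemia should be prescribed by the investigator when deemed necessary". Section 6.15 sets no week limit: "Any medication given to treat hyperglycemia and continued for more than 2 weeks is considered a rescue therapy". SAP section 13, which lists departures from the protocol, does not mention the narrower window.

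**The concern.** The definition stops at week 60, while the analysis that depends on it stops at week 96. A drug started for hyperglycemia at week 50 and continued would end the subject's follow-up in the rate model. The same drug started at week 65 would not, and any hypoglycemia that followed would be counted under the randomized treatment. That contradicts the stated rule that post-rescue data are missing.

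The confirmatory logistic model counts events after rescue. The negative binomial model is therefore the planned analysis of this endpoint that removes events after permitted rescue drugs. The per-protocol repeat does not do so: SAP Table 2 removes data only after rescue with an SGLT2 inhibitor, a sulfonylurea or additional metformin. There is also a reproducibility problem. A programmer working from Protocol 6.15 and one working from SAP 7.5.2 would derive different follow-up times and event counts for the same subject.

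**Working it through.** **Step 1: the windows side by side.**

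| Source | Window |
|---|---|
| Protocol 3.3.3.3, rescue may be prescribed | to week 96 |
| Protocol 6.15, rescue definition | no week limit |
| SAP 7.5.2, rescue definition (including metformin) | to week 60 |
| SAP 8.2 and 8.2.1-8.2.2, body weight and SBP models | values to week 60 |
| SAP 8.1, HbA1c models | values to week 60 |
| SAP 8.2.4, hypoglycemia rate model | to week 96 |

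The week-60 limit fits the HbA1c, weight and SBP analyses. It does not fit the hypoglycemia rate model. Under the SAP text, a drug first started after week 60 is never rescue. Nor is one started later than about week 58, because it cannot exceed 2 weeks inside the window. The calendar gap is 96 - 60 = 36 weeks.

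**Step 2: arm size.** The plan gives no figure for rescue. The only plan figure used here is 210 per arm, and it reproduces. With margin 0.35, SD 1.0, one-sided 0.025 and 90% power, n = 2 × (1.960 + 1.282)² × 1.0² / 0.35² ≈ 171.5, so 172. Then 172 / (1 - 0.18) = 209.8, so 210.

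**Step 3: subject-time wrongly kept.** Assumptions: a fraction p of an arm starts rescue after week 60, starts are uniform over weeks 60-96, and follow-up is otherwise complete. Mean post-rescue time kept is 36 / 2 = 18 weeks per such subject. Full follow-up is 210 × 96 = 20,160 subject-weeks.

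| p (assumed) | Subjects per arm | Subject-weeks kept | Share of full follow-up |
|---|---|---|---|
| 5% | 10.5 | 189 | 0.9% |
| 10% | 21 | 378 | 1.9% |
| 20% | 42 | 756 | 3.8% |

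**Step 4: effect on the rate ratio.** Suppose rescue multiplies the event rate by m (assumed) and the rate is otherwise constant. Each arm's rate is then inflated by f(p) = 1 + p × 18 × (m - 1) / 96, and the bexagliflozin/glimepiride rate ratio is multiplied by f(p for bexagliflozin) / f(p for glimepiride).

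For example, with 5% versus 10% and m = 5, f = 1.0375 and 1.075, and the ratio is 1.0375 / 1.075 = 0.965.

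| Late rescue, bexagliflozin vs glimepiride | m = 0.5 | m = 2 | m = 5 |
|---|---|---|---|
| 5% vs 5% | 1.000 | 1.000 | 1.000 |
| 5% vs 10% | 1.005 | 0.991 | 0.965 |
| 5% vs 20% | 1.014 | 0.973 | 0.902 |

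Equal late rescue leaves the ratio unchanged. If more glimepiride subjects are rescued late and rescue raises the event rate, the error favors bexagliflozin. If rescue lowers the event rate, the direction reverses.

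**The case against.** The mismatch itself is hard to dispute, but there is a fair case that it is small.

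- **Only a sensitivity analysis is affected.** SAP 8.2.3 counts events after rescue in the confirmatory logistic model, so the definition plays no part there. This stands.
- **The stated purpose is different.** SAP 8.2.4 introduces the rate model as a way to account for discontinuation. A reader might infer that it exists to separate study-drug from rescue-drug hypoglycemia, but the SAP does not say so. This stands as to purpose. It does not remove the conflict, because 8.2.4 still states that post-rescue data are missing.
- **The calendar gap overstates the data affected.** A reader might take 36 of 96 weeks (37.5%) as the share of data in error. It is only the stretch of calendar time outside the definition. Step 3 gives 0.9-3.8% of subject-time, and on the 172 per arm left after the planned 18% dropout the 5-20% counts fall to about 9-34 subjects.
- **An arm difference is not established.** A reader might infer one from the ban on glimepiride changes after week 6. That rule binds both arms: bexagliflozin is fixed throughout, and placebo glimepiride has mock titration under the same criteria. Better support lies in Protocol 1.1, which says that sulfonylurea durability can wane, and Protocol 3.2.3, which reports a bexagliflozin effect against placebo of 0.79% at week 24 and 1.02% at week 96. These make unequal late rescue plausible but give no rates.
- **Late rescue is not hidden.** It stays in the concomitant medication summary and listing. Only the separate rescue table (14.1.5.2) and the rescue flag omit it.
- **Protocol 6.15 still supplies a definition after week 60.** True, but Protocol 9.1 makes the SAP the final plan, so the narrower text governs until it is corrected.

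**Conclusion.** The point holds as an internal inconsistency in one sensitivity analysis and in the rescue reporting. As written, SAP 7.5.2 leaves SAP 8.2.4 with nothing to censor after week 60, although 8.2.4 says that such data are missing and the protocol has rescue continuing to week 96. The narrowing is not declared in SAP section 13.

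The size is modest and rests on assumed rescue rates, since the documents give none. With 5-20% late rescue and uniform start times, about 0.9-3.8% of full subject-time is wrongly kept. The rate ratio is multiplied by about 0.965-1.005 for 5% versus 10% late rescue and by 0.90-1.01 for 5% versus 20%, when rescue multiplies the event rate by 0.5-5. It does not move if late rescue is equal in the two arms. The shift of about 10% needs both the 5% versus 20% imbalance and a fivefold event rate after rescue.

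The documents do not support a claim that the key secondary conclusion, type I error or the testing hierarchy is compromised.

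**What to change.** For the 96-week hypoglycemia sensitivity analysis, Table 14.1.5.2 and the rescue flag, define rescue for analysis purposes as either of the following, at any time in the 96-week double-blind treatment period:

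- any medication given to treat hyperglycemia, other than study drug and unchanged background metformin, and continued for more than 2 weeks; or
- metformin intensified for more than 2 weeks.

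Censor at the start date of that medication, so that follow-up in the rate model ends on the last day before it. Both qualifiers in the first item are needed: a definition covering any antihyperglycemic drug taken for more than 2 weeks would literally capture the background metformin that every subject takes.

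Keep the existing week-60 limit for the HbA1c, body weight and SBP analyses. Reconcile Protocol 6.15 with SAP 7.5.2 and 8.2.4, and record any remaining difference from the protocol in SAP section 13. If the week-60 limit was deliberate for the hypoglycemia analysis, 8.2.4 should say that later rescue is not censored, and why.

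The cost is a short edit to the SAP before database lock. SAP 7.5 already requires all medications and their dates to be recorded through treatment and follow-up, so no new data are needed, and neither the sample size nor the confirmatory analysis changes.

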8. EFFICACY

Efficacy data include HbA_{1c}, FPG, body weight, SBP, and hypoglycemia event.

8.1. PRIMARY EFFICACY ENDPOINT AND ANALYSIS

The primary efficacy hypothesis is that bexagliflozin is non-inferior to glimepiride in reducing HbA_{1c} after 60 weeks of treatment. For all analysis of primary efficacy endpoint, all post-baseline values up to week 60 will be used. All visits, including visits after 60 weeks, will be summarized.

8.1.1. Primary Efficacy Analysis

Let $\mu_{\text{bexagliflozin}}$ and $\mu_{\text{glimepiride}}$ represent the mean changes from baseline in HbA_{1c} at Week 60 for bexagliflozin and comparator groups, respectively. The following hypotheses will be tested:

$$H_0: \mu_{\text{bexagliflozin}} - \mu_{\text{glimepiride}} > \delta \text{ versus}$$

$$H_1: \mu_{\text{bexagliflozin}} - \mu_{\text{glimepiride}} \leq \delta$$

Non-inferiority margin δ is chosen to be 0.35% using clinical judgment, with reference to relevant regulatory guidance, and justified by published glimepiride efficacy study (Charpentier et al. 2001).

This hypothesis will be tested based on ITT analysis set. Missing data will be imputed via multiple imputations, following which the MMRM will be repeated on the complete datasets with results combined across complete datasets using standard multiple imputations techniques; HbA_{1c} values collected after the start of rescue medication will not be excluded. A pattern-mixture model will be used to explore the impact of the missing data. Imputation will be conducted within each treatment arm and subgroup (treatment completer vs. treatment terminated early) under the assumption that non-adherent subjects with missing data will follow the same trajectory of non-adherent subjects with values observed. All efforts will be made to retain subjects in the study. If treatment is discontinued, subjects are encouraged to remain in the study and complete all scheduled visits, including final follow-up visit. However, with all efforts, insufficient values may be available for reliable imputation. This analysis will be performed only if $\geq 3\%$ (approximately 6) of subjects in each treatment arm completed scheduled week 60 visit after treatment is stopped. This number is chosen to allow sufficient data to establish a regression model for imputation. For this analysis, the following three-step approach outlined below will be used:

1. Non-monotone (intermediate visits) missing data will be imputed first using the Monte Carlo Markov Chain (MCMC) method under the MAR assumption in all

treatment arms (using the MCMC statement in PROC MI). Multiple chains option (CHAIN=MULTIPLE option in the MCMC statement of PROC MI) will be used. For the non-monotone imputation of the HbA_{1c} missing data, a multivariate normal model will be used including variables for the HbA_{1c} at baseline and all post-baseline visits within each treatment group. Five hundred imputed datasets will be generated.

2. After the non-monotone missing data have been imputed, the remaining monotone missing data will be imputed within each treatment arm and subgroup, defined by whether subject completed 60 week of study treatment, using regression approach. The predictors for the regression imputation model at any time point will be region, treatment background (metformin only or metformin and OHA), baseline eGRF (≥ 90 or < 90 ml/min/1.73 m²), and HbA_{1c} at all previous time points, including baseline. Imputations will be performed using a sequence of regression-based imputations (using PROC MI statement MONOTONE REG) at each post-baseline time point.
3. Imputed data in each of the multiple imputed datasets will be analyzed using a mixed model repeated measures (MMRM) approach. The MMRM model will include region, terms for treatment background (metformin only or metformin and OHA), baseline eGRF (≥ 90 or < 90 ml/min/1.73 m²), treatment, visit, treatment-by-visit interaction, and the baseline HbA_{1c} value, as a fixed effect covariate. The analysis will evaluate the mean change from baseline in HbA_{1c} over the 60-week double blind treatment period. An unstructured covariance will be used to model the within subject correlation. The Kenward Roger approximation will be used to estimate denominator degrees of freedom. If the model with the unstructured covariance structure does not converge, an autoregressive(1) covariance structure will be used. HbA_{1c} values obtained after the start of rescue medication will not be excluded from the analysis. The treatment and treatment by visit interaction terms allow for comparisons of the treatment groups at each visit, and over week 12 to week 60. Least squares (LS) mean treatment differences between the bexagliflozin group and the placebo group at week 60 will be estimated from the model. The LS mean results from all imputed datasets will be combined using the Rubin's combination rule (PROC MIANALYZE).

If no sufficient week 60 values from treatment discontinued subjects are available for imputation, MMRM analysis as in step 3 will be performed using all available data.

Sample SAS code will be provided in Appendix.

In non-inferiority analysis, a CI is calculated to estimate the range of values in which the treatment difference is likely to lie. This CI is used to provide the basis for drawing the study's conclusions. In this specific test, if the 95% CI lies below the specified non-inferiority margin 0.35%, the results would lead to a conclusion of non-inferiority of

bexagliflozin treatment to glimepiride treatment. Lower HbA_{1c} value indicates improvement on subject diabetes condition. Larger decrease would indicate better treatment effect of bexagliflozin compared to glimepiride. Hence, superiority of bexagliflozin group over glimepiride group at week 60 in HbA_{1c} change from baseline will be declared if the upper bound of 95% CI is less than 0.

Descriptive statistics (n, mean, Q1, median, Q3, SD, minimum, and maximum) will be reported by treatment group and visit, along with the least squares means, differences between LS means, a 2-sided 95% confidence interval for each difference, p-values from the model effects. In addition, the LS means with standard errors of the change from baseline over time and difference between treatment groups with 95% will be presented graphically for the ITT population.

For supportive analyses, regardless of having sufficient week 24 values from treatment discontinued subjects are available for imputation or not, MMRM analysis will be performed using all available data. The primary efficacy endpoint will also be analyzed with all observed available data using MMRM method for the PP analysis set.

